5.3.1 Lifestyle Restrictions

5.3.1.1 Meals and Dietary Restrictions

Participants should maintain a normal diet unless modifications are required to manage an AE such as diarrhea, nausea or vomiting.

5.3.1.2 Contraception

Pembrolizumab may have adverse effects on a fetus in utero. Refer to Appendix 3 for approved methods of contraception.

For this study, male participants will be considered to be of non-reproductive potential if they have azoospermia (whether due to having had a vasectomy or due to an underlying medical condition).

A Phase II, Single-arm Study of Combination Pembrolizumab and Olaparib in the Treatment of Patients with Advanced Cholangiocarcinoma
Version 2.1: 17Mar2023

5.3.2 Pregnancy

If a participant inadvertently becomes pregnant while on treatment with pembrolizumab, the participant will be immediately discontinued from study treatment. The site will contact the participant at least monthly and document the participant's status until the pregnancy has been completed or terminated. The outcome of the pregnancy will be reported to Merck within 2 working days if the outcome is a serious adverse experience (e.g., death, abortion, congenital anomaly, or other disabling or life-threatening complication to the mother or newborn). The study Investigator will make every effort to obtain permission to follow the outcome of the pregnancy and report the condition of the fetus or newborn to Merck. If a male participant impregnates his female partner, the study personnel at the site must be informed immediately and the pregnancy must be reported to Merck and followed as described in Section 7.2.2.

5.3.3 Use in Nursing Women

It is unknown whether pembrolizumab is excreted in human milk. Since many drugs are excreted in human milk, and because of the potential for serious adverse reactions in the nursing infant, participants who are breast-feeding are not eligible for enrollment.

5.4 Trial Treatments

The treatment to be used in this trial is outlined below in Table 2

Table 2 Trial Treatment

Drug	Dose/Potency	Dose Frequency	Route of Administration	Regimen/Treatment Period	Use
Pembrolizumab	200 mg	Q3W	IV infusion	Day 1 of each 3 week cycle	Experimental
Olaparib	300 mg	bid	Oral tablet	continuously	Experimental

5.4.1 Timing of Dose Administration

Trial treatment should be administered on Day 1 of each cycle after all procedures/assessments have been completed as detailed on the Trial Flow Chart (Section 6.0). Trial treatment may be administered up to 3 days before or after the scheduled Day 1 of each cycle due to administrative reasons.

All trial treatments will be administered on an outpatient basis. There are no pre-medications for olaparib or pembrolizumab.

A Phase II, Single-arm Study of Combination Pembrolizumab and Olaparib in the Treatment of Patients with Advanced Cholangiocarcinoma
Version 2.1: 17Mar2023

Patient will be treated with olaparib at 300 mg by mouth twice per day continuously in combination with pembrolizumab at 200 mg administered intravenously every three weeks. Sites should make every effort to target infusion timing to be as close to 30 minutes as possible. However, given the variability of infusion pumps from site to site, a window of -5 minutes and +10 minutes is permitted (i.e., infusion time is 30 minutes: -5 min/+10 min).

The Pharmacy Manual contains specific instructions for the preparation of the pembrolizumab infusion fluid and administration of infusion solution.

5.4.2 Dose Modification and toxicity management for immune-related AEs associated with pembrolizumab

AEs associated with pembrolizumab exposure may represent an immunologic etiology. These immune-related AEs (irAEs) may occur shortly after the first dose or several months after the last dose of pembrolizumab treatment and may affect more than one body system simultaneously. Therefore, early recognition and initiation of treatment is critical to reduce complications. Based on existing clinical study data, most irAEs were reversible and could be managed with interruptions of pembrolizumab, administration of corticosteroids and/or other supportive care. For suspected irAEs, ensure adequate evaluation to confirm etiology or exclude other causes. Additional procedures or tests such as bronchoscopy, endoscopy, skin biopsy may be included as part of the evaluation. Based on the severity of irAEs, withhold or permanently discontinue pembrolizumab and administer corticosteroids. Dose modification and toxicity management guidelines for irAEs associated with pembrolizumab are provided in Table 3. NOTE: During management of any irAEs, Olarparib treatment may continue subject to physician discretion.

Table 3 Dose modification and toxicity management guidelines for immune-related AEs associated with pembrolizumab

General instructions:				
Immune-related AEs	Toxicity grade or conditions (CTCAE v4.0)	Action taken to pembrolizumab	irAE management with corticosteroid and/or other therapies	Monitor and follow-up
Pneumonitis	Grade 2	Withhold	
 Administer corticosteroids (initial dose of 1-2 mg/kg prednisone or equivalent) followed by taper 	
 Monitor participants for signs and symptoms of pneumonitis Evaluate participants with suspected pneumonitis with radiographic imaging and initiate corticosteroid treatment Add prophylactic antibiotics for opportunistic infections
	Grade 3 or 4, or recurrent Grade 2	Permanently discontinue		
Diarrhea / Colitis	Grade 2 or 3	Withhold	
 Administer corticosteroids (initial dose of 1-2 mg/kg prednisone or equivalent) followed by taper 	
 Monitor participants for signs and symptoms of enterocolitis (i.e., diarrhea, abdominal pain, blood or mucus in stool with or without fever) and of bowel perforation (i.e., peritoneal signs and ileus).

A Phase II, Single-arm Study of Combination Pembrolizumab and Olaparib in the Treatment of Patients with Advanced Cholangiocarcinoma
 Version 2.1: 17Mar2023

	Grade 4	Permanently discontinue		
 Participants with \geq Grade 2 diarrhea suspecting colitis should consider GI consultation and performing endoscopy to rule out colitis. Participants with diarrhea/colitis should be advised to drink liberal quantities of clear fluids. If sufficient oral fluid intake is not feasible, fluid and electrolytes should be substituted via IV infusion.
AST / ALT elevation or Increased bilirubin	Grade 2	Withhold	
 Administer corticosteroids (initial dose of 0.5- 1 mg/kg prednisone or equivalent) followed by taper 	
 Monitor with liver function tests (consider weekly or more frequently until liver enzyme value returned to baseline or is stable
	Grade 3 or 4	Permanently discontinue	
 Administer corticosteroids (initial dose of 1-2 mg/kg prednisone or equivalent) followed by taper 	
Type 1 diabetes mellitus (T1DM) or Hyperglycemia	Newly onset T1DM or Grade 3 or 4 hyperglycemia associated with evidence of β -cell failure	Withhold	
 Initiate insulin replacement therapy for participants with T1DM Administer anti-hyperglycemic in participants with hyperglycemia 	
 Monitor participants for hyperglycemia or other signs and symptoms of diabetes.
Hypophysitis	Grade 2	Withhold	
 Administer corticosteroids and initiate hormonal replacements as clinically indicated. 	
 Monitor for signs and symptoms of hypophysitis (including hypopituitarism and adrenal insufficiency)
	Grade 3 or 4	Withhold or permanently discontinue ¹		
Hyperthyroidism	Grade 2	Continue	
 Treat with non-selective beta-blockers (e.g., propranolol) or thionamides as appropriate 	
 Monitor for signs and symptoms of thyroid disorders.
	Grade 3 or 4	Withhold or permanently discontinue ¹		
Hypothyroidism	Grade 2-4	Continue	
 Initiate thyroid replacement hormones (e.g., levothyroxine or liothyronine) per standard of care 	
 Monitor for signs and symptoms of thyroid disorders.

A Phase II, Single-arm Study of Combination Pembrolizumab and Olaparib in the Treatment of Patients with Advanced Cholangiocarcinoma
 Version 2.1: 17Mar2023

Nephritis and Renal dysfunction	Grade 2	Withhold	
 Administer corticosteroids (prednisone 1-2 mg/kg or equivalent) followed by taper. 	
 Monitor changes of renal function
	Grade 3 or 4	Permanently discontinue		
Myocarditis	Grade 1 or 2	Withhold	
 Based on severity of AE administer corticosteroids 	
 Ensure adequate evaluation to confirm etiology and/or exclude other causes
	Grade 3 or 4	Permanently discontinue		
All other immune-related AEs	Intolerable/persistent Grade 2	Withhold	
 Based on type and severity of AE administer corticosteroids 	
 Ensure adequate evaluation to confirm etiology and/or exclude other causes
	Grade 3	Withhold or discontinue based on the type of event. Events that require discontinuation include and not limited to: Guillain-Barre Syndrome, encephalitis		
	Grade 4 or recurrent Grade 3	Permanently discontinue		

1. Withhold or permanently discontinue pembrolizumab is at the discretion of the investigator or treating physician.

NOTE:
 For participants with Grade 3 or 4 immune-related endocrinopathies where withhold of pembrolizumab is required, pembrolizumab may be resumed when AE resolves to \leq Grade 2 and is controlled with hormonal replacement therapy or achieved metabolic control (in case of T1DM).

Dose modification and toxicity management of infusion-reactions related to pembrolizumab

Pembrolizumab may cause severe or life threatening infusion-reactions including severe hypersensitivity or anaphylaxis. Signs and symptoms usually develop during or shortly after drug infusion and generally resolve completely within 24 hours of completion of infusion. Dose modification and toxicity management guidelines on pembrolizumab associated infusion reaction are provided in Table 4.

Table 4 Pembrolizumab Infusion Reaction Dose modification and Treatment Guidelines

A Phase II, Single-arm Study of Combination Pembrolizumab and Olaparib in the Treatment of Patients with Advanced Cholangiocarcinoma
 Version 2.1: 17Mar2023

NCI CTCAE Grade	Treatment	Premedication at Subsequent Dosing
Grade 1 Mild reaction; infusion interruption not indicated; intervention not indicated	Increase monitoring of vital signs as medically indicated until the participant is deemed medically stable in the opinion of the investigator.	None
Grade 2 Requires therapy or infusion interruption but responds promptly to symptomatic treatment (e.g., antihistamines, NSAIDs, narcotics, IV fluids); prophylactic medications indicated for ≤ 24 hrs.	
Stop Infusion.
 
Additional appropriate medical therapy may include but is not limited to:
 
IV fluids Antihistamines NSAIDs Acetaminophen Narcotics
 
Increase monitoring of vital signs as medically indicated until the participant is deemed medically stable in the opinion of the investigator. If symptoms resolve within 1 hour of stopping drug infusion, the infusion may be restarted at 50% of the original infusion rate (e.g. from 100 mL/hr to 50 mL/hr). Otherwise dosing will be held until symptoms resolve and the participant should be premedicated for the next scheduled dose.
 
Participants who develop Grade 2 toxicity despite adequate premedication should be permanently discontinued from further study drug treatment
	
Participant may be premedicated 1.5 h (± 30 minutes) prior to infusion of _____ with:
 
Diphenhydramine 50 mg po (or equivalent dose of antihistamine). Acetaminophen 500-1000 mg po (or equivalent dose of analgesic).

Grades 3 or 4 Grade 3: Prolonged (i.e., not rapidly responsive to symptomatic medication and/or brief interruption of infusion); recurrence of symptoms following initial improvement; hospitalization indicated for other clinical sequelae (e.g., renal impairment, pulmonary infiltrates) Grade 4: Life-threatening; pressor or ventilatory support indicated	
Stop Infusion.
 
Additional appropriate medical therapy may include but is not limited to:
 
Epinephrine** IV fluids Antihistamines NSAIDs Acetaminophen Narcotics Oxygen Pressors Corticosteroids
 
Increase monitoring of vital signs as medically indicated until the participant is deemed medically stable in the opinion of the investigator. Hospitalization may be indicated.
 
**In cases of anaphylaxis, epinephrine should be used immediately.
 
Participant is permanently discontinued from further study drug treatment.
	No subsequent dosing

A Phase II, Single-arm Study of Combination Pembrolizumab and Olaparib in the Treatment of Patients with Advanced Cholangiocarcinoma

Version 2.1: 17Mar2023

Appropriate resuscitation equipment should be available at the bedside and a physician readily available during the period of drug administration.

For further information, please refer to the Common Terminology Criteria for Adverse Events v4.0 (CTCAE) at <http://ctep.cancer.gov>

Dose Modification of Olaparib

Patients who experienced grade 3 or 4 toxicities attributable to Olaparib will temporarily hold Olaparib treatment until the side effects have improved to grade 1 or baseline, then restart Olaparib the next lower dose level.

Table 5: Olaparib Dose Modifications

Dose level -1	200 mg bid
Dose level -2	100 mg bid

A Phase II, Single-arm Study of Combination Pembrolizumab and Olaparib in the Treatment of

Patients with Advanced Cholangiocarcinoma

Version 2.1: 17Mar2023

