5.6 Participant Withdrawal/Discontinuation Criteria

Participants may discontinue study treatment at any time for any reason or be dropped from the study treatment at the discretion of the investigator should any untoward effect occur. In addition, a participant may be discontinued from study treatment by the investigator or the Sponsor if study treatment is inappropriate, the trial plan is violated, or for administrative and/or other safety reasons. Specific details regarding procedures to be performed at study treatment discontinuation are provided in Section 7.1.4 – Other Procedures.

A participant must be discontinued from study treatment but continue to be monitored in the study for any of the following reasons:

- The participant or participant's legally acceptable representative requests to discontinue study treatment
- Confirmed radiographic disease progression outlined in Section 7.1.2.6
- Any progression or recurrence of any malignancy, or any occurrence of another malignancy that requires active treatment
- Unacceptable adverse experiences as described in Section 5.2.2.
- The participant has a medical condition or personal circumstance that, in the opinion of the investigator and/or sponsor, placed the participant at unnecessary risk from continued administration of study treatment.
- The participant has a confirmed positive serum pregnancy test
- Noncompliance with study treatment or procedure requirements

A Phase II, Single-arm Study of Combination Pembrolizumab and Olaparib in the Treatment of

Patients with Advanced Cholangiocarcinoma

Version 2.1: 17Mar2023

- Recurrent Grade 2 pneumonitis
- Discontinuation of treatment may be considered for participants who have attained a confirmed complete response (CR) and have been treated for at least 8 cycles (at least 24 weeks), receiving 2 doses of pembrolizumab and at least 80% of the planned doses of olaparib beyond the date when the initial CR was declared. These participants may be eligible for second course treatment described in Section 5.2.3.
- The participant is lost to follow-up
- Completion of 35 treatments (approximately 2 years) with pembrolizumab

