Note: The number of treatments is calculated starting with the first dose. Participants who stop the combination or pembrolizumab after receiving 35 doses may be eligible for retreatment if they progress after stopping study treatment provided they meet the requirements detailed in Section 5.2.3. Participants may be retreated in the Second Course Phase (Retreatment) for up to an additional 17 cycles (approximately 1 year).

- Administrative reasons

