	Is a new cancer (that is not a condition of the study) (although not serious per ICH definition, is reportable to the Sponsor within 24 hours and to Merck within 2 working days to meet certain local requirements); or	
	Is an overdose (whether accidental or intentional). Any adverse event associated with an overdose is considered a serious adverse event for collection purposes. An overdose that is not associated with an adverse event is considered a non-serious event of clinical interest and must be reported within 24 hours to the Sponsor and to Merck within 2 working days..	

A Phase II, Single-arm Study of Combination Pembrolizumab and Olaparib in the Treatment of Patients with Advanced Cholangiocarcinoma
 Version 2.1: 17Mar2023

	Other important medical events that may not result in death, not be life threatening, or not require hospitalization may be considered a serious adverse event when, based upon appropriate medical judgment, the event may jeopardize the participant and may require medical or surgical intervention to prevent one of the outcomes listed previously (designated above by a †).						
Duration	Record the start and stop dates of the adverse event. If less than 1 day, indicate the appropriate length of time and units						
Action taken	Did the adverse event cause Merck product to be discontinued?						

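### The sections disagree on whether olaparib stops with pembrolizumab (recurrent Grade 2 pneumonitis, 35-dose rule), and AE causality and action taken are not required by drug

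*Combined protocol and SAP*

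**What the plan says.** **Dose rules (Section 5.4.2).** Table 3 has a single action column, headed "Action taken to pembrolizumab". In its pneumonitis row, "Grade 3 or 4, or recurrent Grade 2" leads to permanent discontinuation. The note introducing the table reads: "During management of any irAEs, Olarparib treatment may continue subject to physician discretion". Olaparib has its own hold-and-reduce rule, which is triggered by Grade 3 or 4 toxicity judged to be due to olaparib (text above the olaparib dose table). Section 5.5.3 limits the Table 3 guidance to events that the investigator judges related to pembrolizumab. In Table 4, on pembrolizumab infusion reactions, the Grade 3–4 entry ends: "Participant is permanently discontinued from further study drug treatment".

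**Stopping rules (Section 5.6).** The list opens: "A participant must be discontinued from study treatment but continue to be monitored in the study for any of the following reasons". It includes recurrent Grade 2 pneumonitis, unacceptable adverse experiences (with a reference to Section 5.2.2) and "Completion of 35 treatments (approximately 2 years) with pembrolizumab". The note beneath says: "Participants who stop the combination or pembrolizumab after receiving 35 doses may be eligible for retreatment".

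**AE record and analysis.** The action-taken item in Table 7 (Section 7.2.4) is: "Did the adverse event cause Merck product to be discontinued". Its causality item is a single yes/no answer, also about *Merck product*. Sections 9.1.1.1.1 and 9.1.1.2.1 say that Merck supplies both drugs. Section 8.2.1 summarises safety by severity and by relationship to *study drug*, in the singular and undefined.

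**The concern.** Two sites could each follow the protocol and treat the same event differently, one continuing olaparib and the other stopping both drugs. Their participants would then have different exposure and could have different end-of-treatment dates. That date starts the 30-day safety visit (7.1.5.1), the 30- and 90-day reporting windows (7.2) and the discontinuation scan (7.1.2.6.3). None of these sections says which drug's last dose counts when the two stop on different days.

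The AE record raises a related problem. Safety and tolerability of the combination is a secondary objective in 3.2, and 4.5.1 calls it a primary endpoint. A reader of the results will want to know how often each drug was held, reduced or stopped, and for which events. The plan makes dosing decisions on a drug-specific judgement but does not ask for that judgement to be recorded or reported by drug.

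**Working it through.** No arithmetic decides this point, and the plan gives no figure to reproduce. The check sets the passages side by side.

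**1. Recurrent Grade 2 pneumonitis**

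| Source | Pembrolizumab | Olaparib |
|---|---|---|
| Table 3 and the 5.4.2 note | permanently discontinued | may continue, at the physician's discretion |
| 5.6 list | *study treatment* must stop | must stop, if *study treatment* includes it |

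No section defines *study treatment* by drug. Table 2, headed *Trial Treatment*, lists both drugs, which favours reading it as the pair. On that reading 5.6 removes a discretion that 5.4.2 grants. If it means pembrolizumab alone, the two agree, but 5.6 then says nothing about olaparib for any reason on its list.

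**2. Thirty-five doses.** The 5.6 bullet stops *study treatment* at 35 pembrolizumab treatments, while the note contemplates stopping either the combination or pembrolizumab alone. Section 5.4.3.1 counts 35 administrations of *study treatment* as about 2 years. That fits pembrolizumab (35 × 3 weeks = 105 weeks) but not olaparib, where 35 twice-daily doses last 35 / 2 = 17.5 days. So the same term points to pembrolizumab here and to both drugs under Table 2.

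**3. Other adverse events.** Section 5.6 refers to a Section 5.2.2, but 5.2 is the inclusion criteria and has no subsections. Section 5.5.3 uses the same number for Table 3, so 5.4.2 is probably meant. How far the conflict extends depends on that reading:
- Six Table 3 entries require permanent discontinuation of pembrolizumab outright: pneumonitis, diarrhea/colitis, AST/ALT or bilirubin, nephritis, myocarditis, and other immune-related events at Grade 4 or recurrent Grade 3.
- Three more allow withholding or discontinuation: hypophysitis, hyperthyroidism, and other immune-related events at Grade 3.
- Only recurrent Grade 2 pneumonitis is named in both Table 3 and 5.6. The rest conflict with 5.6 only if the broken reference means Table 3 and these entries count as unacceptable.

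**4. Table 4.** *Study drug treatment* does not name a drug. Section 9.1.1.1.7 says infusion reactions are not considered immune mediated, so the 5.4.2 note does not govern them. The wording is ambiguous, not contradictory.

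**5. AE record.** The olaparib rule and 5.5.3 each need a judgement about one drug. Table 7 asks one causality question and one discontinuation question about a term that covers both. Dose reduction appears only in the dechallenge item, which is a causality aid and is also undivided. That item has no clear answer when pembrolizumab is withheld and olaparib continues, which 5.4.2 permits. Section 7.1.2.1 asks for action taken, but on *trial treatment* as a whole.

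**The case against.** **Section 5.6 is specific and mandatory; the 5.4.2 note is general and permissive.** One can read the first as limiting the second. That is a fair reading, but no order of precedence is stated, and the note covers any immune-related event without exception.

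**The objective concerns the combination.** Attribution to the regimen can answer it, and with no monotherapy arm a by-drug attribution is investigator opinion. This limits what a by-drug table can prove. It does not remove the need to record a judgement that already drives dosing, or to report holds and reductions for each drug.

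**Follow-up effects are limited.** Section 7.1.2.6.2 ties on-treatment scans to calendar days, and 7.1.2.6.3 carries the same schedule past discontinuation. If *study treatment* means both drugs, its last dose is naturally the later one. Both points reduce the effect on scans. The safety windows still need the rule stated.

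**Few participants will reach 35 doses.** That takes about 2 years, against a hypothesised PFS of 24 weeks in 3.2. This bears on frequency, not on the inconsistency.

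A reader might infer two stronger things:
- **That toxicity cannot be assigned to a drug.** The documents do not support this. The olaparib rule and 5.5.3 require exactly that attribution, supply records are kept for each drug (9.1.1.1.5, 9.1.1.2.4), and the case report form is not in the documents.
- **That about 4 participants would meet the conflict.** This comes from applying the 11.9% discontinuation rate in 4.2.1.2.1 to 33–36 participants (0.119 × 33 = 3.9; 0.119 × 36 = 4.3). That rate covers all adverse event discontinuations on pembrolizumab in its approved indications. It is not the rate of recurrent Grade 2 pneumonitis, nor of immune-related events alone.

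**Conclusion.** The point holds in a limited form. The text gives conflicting directions for olaparib in one named adverse event, on the reading that *study treatment* includes both drugs, and is internally inconsistent about what stops at 35 pembrolizumab doses. For other adverse events the position is unclear because of a broken cross-reference, and Table 4 is ambiguous. Separately, Table 7 and 8.2.1 as written do not require causality or action taken by drug, and Table 7's action-taken item covers discontinuation only.

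The documents give no rate for the conflicting event, so no participant count is offered. The consequences fall on exposure, follow-up windows and by-drug safety summaries. This review takes no position on whether olaparib should continue or stop. The change should be made because sites cannot follow both sections as they stand.

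**What to change.** 1. Reconcile the 5.4.2 note, Table 3, Table 4 and the 5.6 list with its 35-dose note, so that each stopping reason names pembrolizumab, olaparib or both. The sponsor's clinicians decide which.
2. Correct the reference to Section 5.2.2 in 5.6, and the same number in 5.5.3.
3. Define *study treatment*, *study drug* and *Merck product*, and use each consistently. State which drug's last dose starts the safety and follow-up windows when the drugs stop on different dates.
4. In Table 7, record relationship and action taken (none, held, reduced, discontinued) separately for pembrolizumab and olaparib.
5. In 8.2.1, summarise relationship and action taken by drug, alongside the regimen-level tables.

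The cost is amended wording, a second set of AE fields if the case report form lacks them, and slightly more data entry per event. Participants already enrolled may need a retrospective update.
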